8. **Lung Resection:** Subjects with lung volume reduction surgery within the 12 months prior to Screening (Visit 1).
9. **12-Lead ECG:** An abnormal and significant ECG finding from the 12-lead ECG conducted at Visit 1, including the presence of a paced rhythm on a 12-lead electrocardiogram (ECG) which causes the underlying rhythm and ECG to be obscured. Investigators will be provided with ECG reviews conducted by a centralized independent cardiologist to assist in evaluation of subject eligibility. Specific ECG findings that precluded subject eligibility are listed in [Appendix 3](#): The study investigator will determine the medical significance of any ECG abnormalities not listed in [Appendix 3](#).
10. **Screening Labs:** Significantly abnormal findings from clinical chemistry and haematology tests at Visit 1.
11. **Medications Prior to Spirometry:** Unable to withhold albuterol/salbutamol for the 4 hour period required prior to spirometry testing at each study visit.

12. Medications Prior to Screening: Use of the following medications according to the following defined time intervals prior to Visit 1; ([Table 1](#))

Table 1 Time Interval for Prohibited Medication Prior to Visit 1

Medication	Time Interval Prior to Visit 1
Depot corticosteroids	12 weeks
Systemic, oral, parenteral (intra-articular) corticosteroids	4 weeks
Antibiotics (for lower respiratory tract infection)	4 weeks
ICS/LABA combination products if ICS/LABA therapy is discontinued completely	30 days
Use of ICS at a dose >1000mcg/day of fluticasone propionate or equivalent ¹	30 days
Initiation or discontinuation of ICS use ¹	30 days
Phosphodiesterase 4 (PDE4) inhibitors (e.g. roflumilast)	14 days
Long-acting anticholinergics (e.g., tiotropium and aclidinium, glycopyrionium)	7 days
Theophyllines ²	12 hours (stable dose of theophylline alone is allowed during the study but must be withheld 12 hours prior to each study visit)
Oral leukotriene inhibitors (zaflurkast, montelukast, zileuton)	48 hours
Oral beta ₂ -agonists	
Long- acting	48 hours
Short –acting	12 hours
Olodaterol and Indacaterol (inhaled long-acting beta ₂ -agonist)	14 days
Salmeterol, formoterol, (inhaled long-acting beta ₂ -agonist)	48 hours
LABA/inhaled corticosteroid (ICS) combination products only if discontinuing LABA therapy and switching to ICS monotherapy ³	48 hours for LABA component
Inhaled sodium cromoglycate or nedocromil sodium	24 hours
Inhaled short acting beta2-agonists ⁴	4 hours

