10.1.4. Programmed Checks to Identify Medication Deviations

Medications will be classified into Respiratory Medication Class (RMC) as identified in concomitant medications part of Section 10.6.3.

Following agreement of the correct classification, medications taken prior to or on-treatment (i.e. medication start date on or before treatment stop date) in the intervals identified in Table 12 will be reviewed to identify data which should be excluded from analysis. If the disallowed medication started within the specified window prior to Visit 2 the deviation will be considered full and the subject will be excluded from the PP population. Otherwise the deviation will be considered partial and the subject's data will be excluded from PP analyses from the start of the disallowed medication onwards.

Table 12 Programmed medication checks

| RMC | Disallowed rule |
|--|--|
| Depot corticosteroids | Started on-treatment; stopped after 12 weeks prior to V1 |
| Systemic, oral, parenteral and intra-articular corticosteroids | Started on-treatment; stopped after 4 weeks prior to V1. |
| Antibiotics ¹ | Stopped after 4 weeks prior to V1, and reason is LRTI ¹ |
| ICS ² | Started on-treatment; stopped after 30 days prior to V1 ² |
| PDE4 inhibitors | Started on-treatment; stopped after 14 days prior to V1 |
| Long-acting anticholinergics | Started on-treatment; stopped after 7 days prior to V1 |
| Xanthines | Started on-treatment; stopped after 12 hours prior to each visit |
| Leukotriene receptor antagonists | Started on-treatment; stopped after 2 days prior to V1 |
| Oral beta-2 agonists – long acting ³ | Started on-treatment; stopped after 2 days prior to V1 |
| Oral beta-2 agonists - short-acting | Started on-treatment; stopped after day of V1 |
| Inhaled beta-2 agonists – long acting ³ | Started on-treatment; stopped after 2 days prior to V1 |
| Nedocromil or sodium cromoglycate | Started on-treatment; stopped after 1 day prior to V1 and route is inhaled |
| Other investigational medication for COPD | Started on-treatment; stopped after 30 days prior to V1 |
| Any investigational medication | 30 days or 5 half lives, whichever is longer |
| Oxygen | Greater than 12 hours a day |
| Herbal medicine for respiratory diseases | Manual Review |

1. All antibiotics will be identified; manual review to identify those with reason for administration of LRTI. After v1, antibiotics used for acute infection <=2weeks is permitted.

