2. All ICS will be identified; manual review to identify ICS:

Started but not as switch from ICS/LABA or not within allowed dose range

Dose>1000 mcg fluticasone propionate or equivalent

Stopped with no change to an alternative steroid in the same dose range within 14 days of stopping

Change dose before treatment or change of more than one dose range on the treatment

3. The definition of LABA has now changed and split in to three categories which are now:

'Long-acting beta-2 agonist – Group 1';

'Long-acting beta-2 agonist – Group 2 (Olodaterol or Indacaterol)';
'Long-acting beta-2 agonist – Group 3 (Salmeterol and Formoterol)';

The final decision on exclusion will be made following manual review and will be documented prior to unblinding.

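### The programmed per-protocol check in SAP Table 12 applies a 2-day pre-Visit 1 rule to every inhaled LABA, while protocol Table 1 sets 14 days for olodaterol and indacaterol

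*SAP*

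**What the plan says.** **Protocol.** Section 4.3, Table 1, lists the medication-free intervals required before Visit 1. Inhaled long-acting beta-2 agonists appear in two rows. The row beginning "Olodaterol and Indacaterol (inhaled long-acting beta" carries 14 days. The row beginning "Salmeterol, formoterol, (inhaled long-acting beta" carries 48 hours.

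**SAP check.** Section 10.1.4, Table 12, has one row for "Inhaled beta-2 agonists – long acting". Its disallowed rule is "Started on-treatment; stopped after 2 days prior to V1". The text above the table says that medications taken "in the intervals identified in Table 12 will be reviewed to identify data which should be excluded from analysis".

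**SAP footnote 3.** This footnote is attached to that row and to the oral long-acting row. It reads "The definition of LABA has now changed and split in to three categories which are now", and then names Group 1 with no drugs listed, Group 2 (olodaterol or indacaterol) and Group 3 (salmeterol and formoterol). It gives no interval for any group.

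**Other routes out of PP.** SAP Table 10 makes failure of the prior-medication exclusion criterion a full deviation, and section 10.1.2 removes full deviations from the PP population. Section 4.1 adds deviation tracking during the study and a data review before unblinding.

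**The concern.** The SAP treats a breach of the prior-medication criterion as one that affects the primary outcome. Yet its programmed check uses a shorter interval than the protocol for two named drugs. This is a written rule that conflicts with the protocol, not a detail left for later. A subject who last took olodaterol or indacaterol a week before Visit 1 breaches protocol Table 1 but passes Table 12.

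What is at stake is membership of the PP population, which repeats the primary analysis as a supportive check. If the programmed check is looser than the criterion it is meant to test, the PP set can differ from its own definition without anyone having decided that it should.

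**Working it through.** The plan gives no calculated figure to reproduce here. The check is a comparison of intervals.

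**Step 1. Set the pre-Visit 1 intervals side by side.**

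| Class | Protocol Table 1 | SAP Table 12 | Agree? |
|---|---|---|---|
| Depot corticosteroids | 12 weeks | 12 weeks | Yes |
| Systemic corticosteroids | 4 weeks | 4 weeks | Yes |
| Antibiotics for lower respiratory infection | 4 weeks | 4 weeks | Yes |
| PDE4 inhibitors | 14 days | 14 days | Yes |
| Long-acting anticholinergics | 7 days | 7 days | Yes |
| Leukotriene antagonists | 48 hours | 2 days | Yes |
| Oral long-acting beta-2 agonists | 48 hours | 2 days | Yes |
| Inhaled cromoglycate or nedocromil | 24 hours | 1 day | Yes |
| Salmeterol, formoterol | 48 hours | 2 days | Yes |
| Olodaterol, indacaterol | 14 days | 2 days | **No** |

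Among these rows, the inhaled LABA row is the only one out of line, and only for two of the drugs it covers.

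**Step 2. Size the gap.** Let *d* be the number of whole days from last use to Visit 1.

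- Shortfall = 14 − 2 = 12 days.
- Limits read as inclusive: the protocol is breached when *d* ≤ 14 and the check flags *d* ≤ 2. Missed: *d* = 3 to 14, which is 12 days.
- Limits read as strict: the protocol is breached when *d* < 14 and the check flags *d* < 2. Missed: *d* = 2 to 13, which is 12 days.

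**Step 3. Ask whether the rest of section 10.1.4 closes the gap.** Footnotes 1 and 2 say that all antibiotics and all ICS will be identified and then reviewed manually. Footnote 3 has no such instruction for LABAs. The manual review in this section is therefore framed by the Table 12 intervals, and for inhaled LABAs the only interval written is 2 days.

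**Step 4. Ask whether the rest of the SAP closes the gap.** In part. A subject leaves PP regardless of Table 12 if the site recorded the failed criterion (Table 10). Section 4.1 also provides a review before unblinding that is not limited to the Table 12 intervals. A breach stays undetected only if it falls in the Step 2 band and both of these routes miss it.

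**Step 5. Check that the data exist for a wider window.** Protocol section 5.6 records COPD medications used from 30 days before Visit 0 onward. Visit 0 is on or before Visit 1, so the 14 days before Visit 1 are covered.

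**The case against.** A reader might infer from the mismatch that ineligible subjects will pass into the PP population and will never be flagged. The documents do not support that. Table 12 is one of several routes. A breach recorded as a criterion failure is already a full deviation under Table 10. Section 4.1 requires deviations that may lead to exclusion to be captured before unblinding, and the medication dates that review needs are in the eCRF. This objection stands, and it limits the point to breaches that neither route captures. It does not remove the point. Eligibility deviations are not permitted, so a breach the site recognises should stop enrolment. The programmed check matters most for breaches visible only in the medication dates.

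A reader might also take the 2-day rule as a deliberate analysis choice. The text points the other way. SAP section 10.6.2 uses the three LABA groups in the medication classification, then combines them for the concomitant medication tables. Groups 2 and 3 match the two inhaled LABA rows of protocol Table 1. The likelier explanation is that the groups were created for this check and the printed row was not updated. That is an inference, but it makes a drafting omission at least as plausible as a decision.

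The practical effect is also small. The FEV1 eligibility limit is an upper bound (at most 70% of predicted), so any residual bronchodilation would make it harder to meet. Adding the 7 to 14 day run-in to last use on days 3 to 14 puts last use 3 + 7 = 10 to 14 + 14 = 28 days before the Day 1 baseline. This stands as a reason to rate the point low.

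**Conclusion.** The inconsistency holds as written: 2 days in SAP Table 12 against 14 days in protocol Table 1 for olodaterol and indacaterol, with footnote 3 creating Group 2 but giving it no interval. The programmed check alone misses a band of about 12 days, either days 3 to 14 or days 2 to 13 before Visit 1 depending on how the limits are read. Salmeterol and formoterol are not affected.

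The consequence is conditional. Subjects in that band could remain in PP if the breach was neither recorded under Table 10 nor caught by the section 4.1 review. The documents give no figure for prior olodaterol or indacaterol use, so the number affected is unknown and may be zero. Only the supportive PP analysis of the primary endpoint can change. The Modified ITT analysis is unaffected. This is a minor correction, worth making because it is cheap and must precede unblinding.

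The conclusion assumes that Table 12 would be programmed as printed. If the program already applies separate intervals by group, only the SAP text needs correcting.

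**What to change.** Before unblinding:

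- Reconcile the Table 12 inhaled LABA row with protocol Table 1 by footnote 3 group, so that the Group 2 check uses the interval the protocol already states and Group 3 stays at 48 hours. If the difference is intended, document why.
- State which drugs Group 1 covers and which interval applies. Footnote 3 lists no members, and protocol Table 1 has no row under that label.
- State whether footnote 3 is meant to change the oral long-acting row, where it also appears. The interval there already agrees with the protocol.

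The cost is a short edit to Table 12 and its footnote and a matching change to the deviation program. No new data are needed. The downside is that a few more subjects may leave the PP set.

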10.2. Appendix 2: Time & Events

10.2.1. Protocol Defined Time & Events

| Visit | Run-in | Double-blind treatment period | | | | | | | | | | Early Withdrawal (EW) Visit | Follow-Up (Phone contact) |
|---|----------------------|-------------------------------|---------|---------|----------|----------|----------|-----------|-----------|-------------------------|---|------------------------------|---------------------------|
| | | Visit 2 | Visit 3 | Visit 4 | Visit 5 | Visit 6 | Visit 7 | Visit 8 | Visit 9 | Day 169 (Visit 8+1 day) | | | |
| Day | Visit 0 (Pre-Screen) | Day -7 to -14 | Day 1 | Day 2 | Day 28±2 | Day 56±4 | Day 84±4 | Day 112±4 | Day 168±4 | Day 169 (Visit 8+1 day) | | 7±2 days after Visit 9 or EW | |
| Week | | -1 | 0 | 0 | 4 | 8 | 12 | 16 | 24 | | | | |
| Written Informed Consent ¹ | x | | | | | | | | | | | | |
| Demography/ COPD History | X | | | | | | | | | | | | |
| Medical History | | X | | | | | | | | | | | |
| Physical Examination | X | | | | | | | | | X | | X | |
| Smoking Status | X | | | | | | | | | X | | X | |
| Smoking Cessation Counselling | X | | | | | | | | | X | | X | |
| Chest X-ray ² | X | | | | | | | | | | | | |
| Inclusion/exclusion criteria | X | | | | | | | | | | | | |
| Randomization criteria | | | X | | | | | | | | | | |
| Screening spirometry (including post-bronchodilator testing) ³ | | X | | | | | | | | | | | |
| mMRC questionnaire | | X | | | | | | | | | | | |
| Register visit in IVSR | x | x | x | x | x | x | x | x | x | x | x | x | |
| Diary Card Dispense or Collection/Review | | X | X | X | X | X | X | X | X | X | X | | |

| Visit | Run-in | Double-blind treatment period | | | | | | | | | | Early Withdrawal (EW) Visit | Follow-Up (Phone contact) |
|--|----------------------|-------------------------------|----------------|---------|----------|----------|----------|-----------|-----------|-------------------------|---|------------------------------|---------------------------|
| | | Visit 2 | Visit 3 | Visit 4 | Visit 5 | Visit 6 | Visit 7 | Visit 8 | Visit 9 | Day 169 (Visit 8+1 day) | | | |
| Day | Visit 0 (Pre-Screen) | Day -7 to -14 | Day 1 | Day 2 | Day 28±2 | Day 56±4 | Day 84±4 | Day 112±4 | Day 168±4 | Day 169 (Visit 8+1 day) | | 7±2 days after Visit 9 or EW | |
| Week | | -1 | 0 | 0 | 4 | 8 | 12 | 16 | 24 | | | | |
| Efficacy assessments | | | | | | | | | | | | | |
| Trough Spirometry ⁴ | | | | X | X | X | X | X | X | X | | | |
| Serial Spirometry ⁵ | | | X | | | | | | | | | | |
| COPD exacerbation assessment | x | X | X | X | X | X | X | X | X | X | X | X | |
| Baseline Dyspnea Index (BDI) | | | X | | | | | | | | | | |
| Transition Dyspnea Index (TDI) | | | | X | | | X | | | X | | | |
| SGRQ | | X | | X | | X | | X | | X | | | |
| COPD Assessment Test (CAT) | | X | | X | | X | | X | | X | | | |
| Healthcare resource utilization ⁶ | | | | | | | | | | | | | |
| Safety Assessments | | | | | | | | | | | | | |
| 12-Lead ECG | | X | X ⁷ | | | | | | | X ⁷ | | X | |
| Vital Signs (blood pressure and pulse rate) ⁸ | | X | X | X | X | X | X | X | X | X | X | X | |
| Adverse Event /Con-Med Assessment | | X | X | X | X | X | X | X | X | X | X | X | |
| Laboratory Assessments | | | | | | | | | | | | | |
| Pharmacogenetics sample ⁹ | | | X | | | | | | | | | | |
| Routine urine | | X | | | | | | | | X | | X | |
| Urine Pregnancy Test | | X | X | | | | X | | X | | X | X | |
| Clinical Laboratory tests ¹⁰ | | X | | | | X | | X | | X | | X | |
| Medication | | | | | | | | | | | | | |
| COPD and Concurrent Medication Assessment | x | X | X | X | X | X | X | X | X | X | X | | |

| Visit | Visit 0 (Pre-Screen) | Screening Visit (Visit 1) | Double-blind treatment period | | | | | | | | Early Withdrawal (EW) Visit | Follow-Up (Phone contact) |
|--|----------------------|---------------------------|-------------------------------|---------|----------|----------|----------|-----------|-----------|--------------------------|-----------------------------|------------------------------|
| | | | Visit 2 | Visit 3 | Visit 4 | Visit 5 | Visit 6 | Visit 7 | Visit 8 | Visit 9 | | |
| Day | | Day -7 to -14 | Day 1 | Day 2 | Day 28±2 | Day 56±4 | Day 84±4 | Day 112±4 | Day 168±4 | Day 169 (Visit 8 +1 day) | | 7±2 days after Visit 9 or EW |
| Week | | -1 | 0 | 0 | 4 | 8 | 12 | 16 | 24 | | | |
| Dispense/collect rescue salbutamol/albuterol | | X | X | X | X | X | X | X | X | X | X | |
| Dispense double-blind study drug | | | | X | | X | X | X | | | | |
| Collected double-blind study drug | | | | | X | X | X | X | X | | X | |
| Assess double-blind study drug compliance | | | | | | X | X | X | X | | X | |

1. Written informed consent must be obtained prior to performing any Visit 1 procedures or initiating any alterations in a subject's medications. Subjects will be assigned a study number at the time the ICF is signed. Visit 0 and Visit 1 may occur on the same day if applicable.
2. To be performed only if there is no chest X-ray or CT scan available within 6 months prior to Visit 1
3. Spirometry to be conducted as follows: pre-bronchodilator testing following by post-albuterol/salbutamol testing, followed by post-ipratropium testing. Post albuterol/salbutamol testing conducted 10 to 30 min after subject self-administration of 4 puffs of albuterol/salbutamol via MDI with a spacer. Subject will then self administer 4 puffs of ipratropium bromide via MDI and spacer, followed by spirometry testing 30 to 60 min later.
4. Trough spirometry obtained twice: at 23 and 24 hours after the previous day's morning dose.
5. 6 hr serial spirometry: Performed post-dose at 15 and 30 min and 1, 3 and 6 hours. At Visit 2 (Day 1), pre-dose measurements will be obtained -30min and -5min pre-dose.
6. Healthcare resource utilization will be collected and entered in the e-CRF as required during the study, collection of this data to be aided by the subject documentation in the paper diary of any contact with the doctor or nurse about their lung condition which was unrelated to study participation.
7. ECG conducted pre-dose and 10 and 45 minutes post-dose
8. Vital signs to be measured pre-dose and 10 and 45 minutes post-dose at visit 2, and measured only pre-dose at other visits (prior to spirometry).
9. PGx sample preferably to be obtained at Visit 2 after randomization, but can also be obtained at a subsequent study visit. PGx consent must be obtained prior to sampling.
10. Haematology, and clinical chemistry.

10.3. Appendix 3: Assessment Windows

Data are generally reported according to the nominal time of clinic visits and assessments as specified in the protocol, and time windows for exclusion will not be defined. For example, if a subject recorded values for the Week 4 visit that were actually made on the 21st day of treatment, they will be presented as Week 4 values in the summary tables.

For the 23 and 24 h post-dose trough FEV1 measurements, a time window of 22.5-24.5 h is allowed for the actual time of an assessment relative to time of dosing. Values falling outside of this window will not be used in the PP analysis of the primary endpoint, but will still be included in all Modified ITT analyses.

10.4. Appendix 4: Treatment States and Phases

10.4.1. Treatment Phases

Assessments and events will be classified according to the time of occurrence relative to study treatment, unless otherwise specified.

| Treatment Phase | Definition |
|-----------------|---|
| Pre-Treatment | Date < Study Treatment Start Date |
| On-Treatment | Study Treatment Start Date ≤ Date ≤ Study Treatment Stop Date |
| Post-Treatment | Date > Study Treatment Stop Date |

NOTES:

- If the study treatment stop date is missing then the assessment will be considered to be On-Treatment

10.4.2. Treatment States

Assessments and events will be classified according to time of occurrence relative to the start and/or stop date of the study treatment.

10.4.2.1. Treatment States for Concomitant Medications Data

| Treatment State | Definition |
|-----------------|---|
| Pre-Treatment | Medication start date < Study Treatment Start Date |
| On-Treatment | Medication start date ≤ Study Treatment Stop Date and Medication stop date ≥ Study Treatment Start Date |
| Post-Treatment | Medication stop date > Study Treatment Stop Date |

NOTES:

- A medication will be classed in every period of the study in which it was taken.
- For medications with partial start and stop dates or missing start/stop dates, the medication will be classed in every period of the study in which it could have been taken.
- If the study treatment stop date is missing then the medication will be considered to be On-Treatment.
- The answers to the questions "Taken Prior to Study?" and "Ongoing?" which are recorded on the eCRF will also be taken into consideration to determine if the medication was started pre-treatment or continued post-treatment. In each case, should the answers suggest a different classification than the dates, the medication will be summarised in all possible classifications (pre/on/post) in which it could conceivably have been taken.

10.4.2.2. Treatment States for AE Data

| Treatment State | Definition |
|--|---|
| Pre-Treatment | AE Start Date < Study Treatment Start Date |
| On-Treatment | Study Treatment Start Date ≤ AE Start Date ≤ Study Treatment Stop +1 |
| Post-Treatment | AE Start Date > Study Treatment Stop Date+1 |
| Onset Time Since 1 st Dose (Days) | If Treatment Start Date > AE Onset Date = AE Onset Date - Treatment Start Date If Treatment Start Date ≤ AE Onset Date = AE Onset Date - Treatment Start Date +1 Missing otherwise. |

| Treatment State | Definition |
|-----------------|--|
| Duration (Days) | AE Resolution Date – AE Onset Date + 1 |
| Drug-related | If relationship is marked 'YES' on Inform/CRF OR value is missing. |

NOTES:

- If the study treatment stop date is missing then the AE will be considered to be On-Treatment.
- If the AE onset date is missing or partial then the AE will be considered on-treatment unless there is evidence to the contrary (e.g. the month of the onset date is present and is less than the month of the first dose of study treatment).
- AEs reported by subjects who did not receive treatment will be considered pre-treatment.
- Any SAEs for screen failures, run-in failures or subjects who were randomised but did not receive treatment will be classified as pre-treatment SAEs.

